9.2.1 Prior to 2nd donation visit

Prior to the second donation visit, participants will receive a courtesy reminder email 7 days before the appointment (see **Annex 2.14** COMPARE Stage 1 2nd visit reminder V1 13.08.2015). The email will reiterate the date of the booked appointment and will provide details of how to make or change appointments and how to contact the study helpdesk with any queries.

9.2.2 Arrival at the mobile donation session

On arrival at the mobile session, the donor carer checks the donor DHC for a temporary message indicating whether a research sample should be collected. The DHC is then placed in the study-specific wallet ready for collection by the screening donor carer.

9.2.3 Donor screening

The screening donor carer collects the study-specific wallet from the welcome desk and checks the DHC for a temporary message.

If the DHC has a temporary message, indicating that a research sample should be taken, the donor carer will:

1. Conduct pre-donation medical screening; if a participant is deferred for reasons other than for low haemoglobin, they will not provide any samples or measurements for the research and their participation in the study will end here
2. Perform a copper sulphate finger prick test (with or without a subsequent venous sample for HemoCue®) in those donors who pass the pre-donation medical screening
3. Perform a haemoglobin measurement on a capillary sample with the HemoCue®. This will be performed at the same time as the copper sulphate test to avoid additional finger pricks
4. Perform a haemoglobin measurement using a non-invasive device (i.e. either the Haemospect® or Orsense NMB200®, whichever is in current use by the mobile team)
5. Collect a research sample if the participant fails the copper sulphate test (if the participant passes the copper sulphate test, the donor will provide the research samples at the donation bed as part of their normal blood donation).

9.2.4 Research Sample Collection

Donors will provide a 4ml EDTA plasma sample

For donors who pass NHSBT's pre-donation test, the 4ml research sample will be collected in from surplus blood routinely collected in the satellite pouch that forms part of the blood collection unit (ie, a separate venepuncture will *not* be required).

The procedures for research sample collection are as described in **Section 9.1.3** however only one 4ml EDTA tube (purple top) will be collected. Thus, in the 'staff use only' box of the DHC the donor carer will indicate that one research sample has been collected.

For donors who fail the standard copper sulphate NHSBT haemoglobin test, the 4ml of blood will be collected from the venepuncture used for the standard secondary (venous HemoCue®) haemoglobin screening test (ie, once again, an additional venepuncture will *not* be required).

9.2.5 Reconciliation of research samples

The donor carer at the reconciliation table will:

1. Separate the research sample tubes and the study wallets (containing the DHC) from the donation packs.
2. Reconcile the number of research samples and DHC forms on a study specific checklist and investigate reasons for non-reconciliation and report these on the checklist.
3. Update PULSE donor records with 'outcome of donation'
Post reconciliation checklists to the NHSBT administration team. NB: If no donors have been recruited, the donor carer will send an email to UK BioCentre, cc'd to the admin team and UoC.
4. Complete a session delivery note and place research sample tubes in appropriate research-specific transport boxes for collection by routine transport staff.
5. Pack samples in transport boxes filled from bottom left backwards then bottom right backwards.

9.2.6 Transport of Samples

The protocol for the transport of research samples from the second donation will be identical to the processes described in **Section 10.1.6**

9.2.7. Post-donation questionnaire

Within two weeks of attending visit 2, Stage 1 donors will receive an email from the UoC Study Data Manager (see **Annex 2.15** COMPARE Email questionnaire (Stage 1, Visit 2) V1 26.10.2015) with an online (URL) link to a study questionnaire. The URL-link will contain a unique custom tag which will be used to anonymously track questionnaire completion and to verify that it has been completed by the intended recipient. The participant will also receive a separate email with the questionnaire password (see **Annex 2.6** COMPARE Email_questionnaire key_V1 13.08.2015). If the participant does not provide their responses to the questionnaire they will be sent an email reminder after 7 days (see **Annex 2.16** COMPARE Email_questionnaire reminder 1 (Stage 1, Visit 2) V1 26.10.2015). A second email reminder will be sent after a further 14 days (see **Annex 2.17** COMPARE Email_questionnaire reminder 2 (Stage 1, visit 2) V1 26.10.2015). If the questionnaire has not been completed 7 days after reminder 2, then a text reminder will be sent (see **Annex 2.9** COMPARE questionnaire text reminder (Stage 1 and Stage 2) V1 17.12.2015)

This very brief questionnaire, which will take no more than 5 minutes to complete will ask the questions contained in Section 3 of the questionnaire shown in **Annex 2.10** COMPARE study questionnaire V3 15.12.2015.

On completion of the questionnaire the participant will be taken to a 'thank you' web page.

For participants who have attended both donation visits, and have completed the questionnaire following visit 2 but have not responded to visit 1 questionnaire, they will receive an email with a URL-link (the password will be sent separately) see **Annex 2.24**, COMPARE Email_questionnaire (Part 1 re-invite, Stage 1) V1 05.07.2016.

For participants who have not completed the questionnaire following either visit but have attended both donation visits, an email invite with a request to complete the baseline questionnaire will be sent – see **Annex 2.25**, COMPARE Email_questionnaire (Part 1 & 2, Stage 1) V1 05.07.2016.

10. Stage 2 study procedures

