Stage 2: One of the new methods to be evaluated (ie, non-invasive spectrometry) involves a choice between two commercially-available devices. It would be ideal to conduct a head-to-head comparison of these two devices in the same set of participants as the other methods are to be compared in. Unfortunately such an approach would likely be too time-consuming and disruptive to NHSBT’s high-throughput service. Hence, we plan a second stage of recruitment that will involve enrolment of a further approximately 13,000 participants, focusing on the comparison of two different non-invasive spectrometry devices. During the second stage of recruitment, selection of mobile donation centres will be done in a way to over-sample donors of non-European ancestry (eg, those of African, Middle Eastern, and South Asian ancestry). The rationale is that the performance of non-invasive spectrometry devices is known to differ in people with different skin colour and tone.

Figure 1: Study design

^a assuming ~30% drop-out rate 18,000 donors need to be recruited at the previous donation visit.

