9.1.7. Post-donation questionnaire

Within two weeks of attending visit 1, Stage 1 donors will receive an email (see **Annex 2.5** COMPARE Email welcome and questionnaire (Stage 1, Visit 1 and Stage 2) V2 26.10.2015) from the UoC Data Manager with an online (URL) link to a study questionnaire. The URL-link will contain a unique custom tag which will be used to anonymously track questionnaire completion and to verify that it has been completed by the intended recipient. The participant will also receive a separate email with the questionnaire password (see **Annex 2.6** COMPARE Email_questionnaire key_V1 13.08.2015). If the participant does not provide their responses to the questionnaire they will be sent an email reminder after 7 days (see **Annex 2.7** COMPARE Email_questionnaire reminder 1 (Stage 1, visit 1 and Stage 2) V2 26.10.2015). A second email reminder will be sent after a further 14 days (see **Annex 2.8** COMPARE Email_questionnaire reminder 2 (Stage 1, visit 1 and Stage 2) V2 26.10.2015). If the questionnaire has not been completed 7 days after reminder 2, then a text reminder will be sent (see **Annex 2.9** COMPARE questionnaire text reminder (Stage 1 and Stage 2) V1 17.12.2015) The questionnaire will include the following questions; more details can be found in **Annex 2.10** COMPARE study questionnaire V3 15.12.2015:

Section 1

Questions about the general demographic characteristics of the participant.

Section 2

The validated Fitzpatrick questionnaire for skin type assessment.

Section 4

Questions regarding the symptoms of iron deficiency.

Section 5

The validated Medical Outcomes Survey SF-36 version 2 for general health and wellbeing.

Section 6

Questions regarding general adverse blood donation outcomes, e.g. breathlessness and fainting, including the validated short-form Blood Donors Reaction Inventory (BDRI).

Section 7

Questions regarding the lifestyle habits of donors, e.g. smoking, alcohol intake, dietary intake in general and of iron-containing foods in particular, and physical activity.

Completion of the study questionnaire is not essential to remain part of the study, however a maximum of two reminder emails will be sent to participants who do not complete it (see above).

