Occupation	Which of the following best describes your current situation	
1 = In full-time employment (paid or unpaid) 2 = In part-time employment (paid or unpaid) 3 = Do not work (e.g. retired, unemployed, student) 999 = don't know / prefer not to answer

SECTION 2: YOUR SKIN COLOURING

The following set of 9 questions will ask you about your individual characteristics that are associated with skin tone (e.g. eye and hair colour). Your answers will help researchers assess the variability in the performance of the non-invasive ('light-shining') haemoglobin devices depending on skin tone.

fitzEyes	Which of the following best describes your natural eye colour? Please choose one that matches you most.	
0 = Light blue, light grey or light green 1 = Blue, grey or green 2 = Hazel or light brown 3 = Dark brown 4 = Brownish black 5 = Don't know / prefer not to answer

fitzHair	Which of the following best describes your natural hair colour? Please choose one that matches you the most.	
0 = Red or light blond 1 = Blond 2 = Dark blond or light brown 3 = Dark brown 4 = Brownish black 5 = Don't know / prefer not to answer

fitzSkin	Which of the following best describes your natural skin colour before sun exposure? Please choose one that matches you the most.	
0 = Ivory white or reddish 1 = Fair or pale 2 = Fair to beige, with golden undertone 3 = Olive or light brown 4 = Dark brown or black 5 = Don't know / prefer not to answer

fitzFreckle	How many freckles do you have on unexposed areas of your skin? Please choose one that matches you the most.	
0 = Many 1 = Several 2 = A few 3 = Very few 4 = None 5 = Don't know / prefer not to answer

fitzBurn	How does your skin respond to spending too long in the sun? Please choose one that matches you the most.	
0 = Always burns, blisters and peels 1 = Often burns, blisters and peels 2 = Burns moderately 3 = Burn rarely, if at all 4 = Never burns 5 = Don't know / prefer not to answer

fitzTan1	To what degree does your skin tan? Please choose one that matches you the most.	
0 = Never, I always burn 1 = I seldom tan 2 = I sometimes tan 3 = I often tan 4 = I always tan 5 = Don't know / prefer not to answer

fitzTan2	Do you tan within several hours after sun exposure? Please choose one that matches you the	
0 = Never 1 = Seldom 2 = Sometimes

	most.	3 = Often 4 = Always 5 = Don't know / prefer not to answer

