fitzFace	How sensitive is your face to the sun? Please choose one that matches you the most.	0 = Very sensitive 1 = Sensitive 2 = Normal 3 = Resistant 4 = Very resistant / never had a problem 5 = Don't know / prefer not to answer
fitzExpose	When did you last expose your body to sun (or artificial sunlamp / tanning cream)?	0 = More than 3 months ago 1 = 2-3 months ago 2 = 1-2 months ago 3 = Less than a month ago 4 = less than 2 weeks ago 5 = Don't know / prefer not to answer

SECTION 3: MEASURING YOUR HAEMOGLOBIN LEVELS		
Cuso41	Thinking about the finger prick test performed before you donate blood, please indicate how much you agree or disagree with the following statements. It reliably measures my haemoglobin levels.	1 = Strongly disagree 2 = Disagree 3 = Somewhat disagree 4 = Neither agree nor disagree 5 = Somewhat agree 6 = Agree 7 = Strongly agree
Cuso42	It is quick to do	1 = Strongly disagree 2 = Disagree 3 = Somewhat disagree 4 = Neither agree nor disagree 5 = Somewhat agree 6 = Agree 7 = Strongly agree
Cuso43	It does not hurt	1 = Strongly disagree 2 = Disagree 3 = Somewhat disagree 4 = Neither agree nor disagree 5 = Somewhat agree 6 = Agree 7 = Strongly agree
Cuso45	Overall it is a good test to measure haemoglobin levels	1 = Strongly disagree 2 = Disagree 3 = Somewhat disagree 4 = Neither agree nor disagree 5 = Somewhat agree 6 = Agree 7 = Strongly agree
Importance1	We would like to know what is important to you with regards to checking your haemoglobin levels before donation. Please rank each statement in order of importance from 1 (most important) to 5 (least important). The blood test should accurately measure my haemoglobin levels.	1 = most important 2 = 2nd most important 3 = 3rd most important 4 = 4th most important 5 = least important
Importance2	The blood test should cause minimal pain and discomfort.	1 = most important 2 = 2nd most important 3 = 3rd most important 4 = 4th most important 5 = least important
Importance3	The blood test should take as	1 = most important

	little time as possible.	2 = 2 nd most important 3 = 3 rd most important 4 = 4 th most important 5 = least important
Importance4	The blood test should cost as little as possible to the blood service.	1 = most important 2 = 2 nd most important 3 = 3 rd most important 4 = 4 th most important 5 = least important

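### In Stage 1 the recent sun-exposure item is asked after visit 1, but the non-invasive reading it should describe is taken at visit 2 and the item is not asked again

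*Protocol*

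**What the plan says.** - **Skin items, Stage 1.** Protocol 9.1.7: "Within two weeks of attending visit 1, Stage 1 donors will receive an email" linking to the main questionnaire. That form includes "The validated Fitzpatrick questionnaire for skin type assessment", which is Section 2 of Annex 2.10.
- **Purpose of the skin items.** Annex 2.10 tells donors: "Your answers will help researchers assess the variability in the performance of the non-invasive" devices according to skin tone. Protocol 4.3.2 lists skin colour tone among the key characteristics in secondary endpoint 5. Protocol 4.2 says that "the performance of non-invasive spectrometry devices is known to differ in people with different skin colour and tone".
- **The item that depends on time.** The last of the nine items, fitzExpose, asks: "When did you last expose your body to sun (or artificial sunlamp / tanning cream"). It has five answer steps, from over 3 months ago (code 0) to under 2 weeks ago (code 4).
- **When the reading is taken.** Protocol 4.2 and Table 2 (Section 8) give Stage 1 donors routine tests only at visit 1. Protocol 9.2.3 places the non-invasive measurement at visit 2. Protocol 9.1.4 books that visit 12 weeks ahead for men and 16 weeks ahead for women.
- **Visit 2 form.** Protocol 9.2.7: it "will ask the questions contained in Section 3 of the questionnaire shown in" Annex 2.10. Section 3 covers donors' views of the haemoglobin tests.
- **Late responders.** Protocol 9.2.7 also sends the main questionnaire again, after visit 2, to donors who attended both visits but did not answer the first time.
- **Stage 2.** Protocol 10.7 sends the whole questionnaire, skin items included, within two weeks of the single visit at which the reading is taken.

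**The concern.** The skin section was added to explain how the light-based devices perform. Most of it concerns lasting traits, so the date of answering hardly matters. fitzExpose differs, because its correct answer changes from week to week. In Stage 1 it is collected at a visit with no device reading and is not collected at the visit that has one.

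Two things follow. If recent exposure is used in a Stage 1 device analysis, the recorded value belongs to another date, and any exposure between the visits is unrecorded. The same code also has three meanings across the study: exposure weeks before the reading (most Stage 1 responders), exposure asked some time after it (re-invited Stage 1 donors), and exposure asked soon after it (Stage 2).

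The timing is fixed by the protocol. A later analysis plan cannot recover exposure at visit 2 if nobody asked about it.

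**Working it through.** The plan states no figure for this, so the check sets the dates side by side.

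**Inputs**
- Visit interval: 12 weeks (men), 16 weeks (women), from 9.1.4.
- Email: up to 2 weeks after visit 1, from 9.1.7.
- Reminders: 7, then 14, then 7 days, from 9.1.7. Total 28 days = 4 weeks.
- Longest delay to answering, taking the text reminder as the last prompt: 2 + 4 = 6 weeks.

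**Lag from answer to reading** = visit interval − delay to answering.

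| Delay to answering | Men | Women |
|---|---|---|
| 0 weeks (emailed and answered at once) | 12 − 0 = 12 weeks | 16 − 0 = 16 weeks |
| 2 weeks (latest email, answered at once) | 12 − 2 = 10 weeks | 16 − 2 = 14 weeks |
| 6 weeks (answered at text reminder) | 12 − 6 = 6 weeks | 16 − 6 = 10 weeks |

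**Lag against the item's scale.** Converting at 30.44 days per month, the lags are 1.38 to 2.76 months for men and 2.30 to 3.68 months for women. The scale's top step begins at 3 months, so the lag covers much or all of it.

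**What happens to a code.** Take a donor exposed within the week before answering (code 4), with no exposure afterwards. At the reading the correct code would be:
- 6-week lag: 2
- 10- or 12-week lag: 1
- 14- or 16-week lag: 0

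A donor exposed again between visits could still belong in code 4. The visit 1 answer cannot separate these cases.

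**Share of the instrument.** The protocol fixes no scoring rule. If the nine items, each scored 0-4, were summed (an assumption), the maximum would be 9 × 4 = 36 and fitzExpose would supply up to 4/36 = 11%.

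**The other eight items.** They ask about natural eye, hair and skin colour, freckles on unexposed skin, habitual burning and tanning, and facial sensitivity. The skin-colour item asks explicitly for natural "skin colour before sun exposure? Please choose one that matches you the most". None should shift materially over 12-16 weeks.

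**Timing if the item were asked after visit 2.** If 9.2.7 carried fitzExpose, the answer would normally come 0-2 weeks after the reading, and about 6 weeks after it for a donor who replies only at the text reminder. This matches Stage 2.

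**The case against.** A reader might infer that the Stage 1 skin-tone analysis as a whole rests on out-of-date data, or that the two stages cannot be pooled or compared on skin type. The documents support neither reading. Eight of the nine items keep their meaning whenever they are asked. On the summing assumption, 32 of the 36 points are unaffected. An error in one item does not by itself bar pooling. How, or whether, the items are scored may be settled in an analysis plan that is not at hand.

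Other points on that side also stand:
- The protocol names skin colour tone as a modifier. It nowhere names recent tanning, and it does not quantify any effect of tanning on device error.
- Stage 2, with about 13,000 donors, focuses on the two devices and over-samples non-European ancestry. Its skin items follow the visit of the reading, so the main skin-colour question is largely protected.
- The roughly 12,500 Stage 1 donors expected at visit 2 are an upper bound on those affected. Completing the questionnaire is optional, and re-invited donors answer after the reading.
- The visit 2 form was kept short on purpose, and moving an item splits an instrument that the protocol calls validated.

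These arguments limit the reach of the point. They do not remove the mismatch: fitzExpose is asked so that readings can be related to skin condition, and Stage 1 asks it at the wrong visit.

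**Conclusion.** The point holds for fitzExpose, and for any total score that includes it, in Stage 1. The recorded value does not describe exposure at the reading and is not like-for-like with Stage 2. For donors who answer within the reminder schedule and attend on time, the answer comes about 6-12 weeks (men) or 10-16 weeks (women) before the reading. Re-invited donors answer after it.

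These ranges assume that visit 2 falls on the booked interval and that nobody answers after the text reminder. The protocol guarantees neither: appointments can be moved, and the reminder is not described as a deadline.

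Analyses by the eight stable items, by constitutive skin type or by ethnicity are little affected. Stage 2 and the primary endpoint are unaffected. Severity is minor: one item, one modifier of a secondary endpoint, one stage. It is worth raising because the repair is nearly free and the lost information cannot be recovered later.

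**What to change.** - In Protocol 9.2.7, add fitzExpose to the visit 2 questionnaire, worded as exposure before the visit 2 reading. Amend Annex 2.10 to match. Keep the other eight skin items from visit 1.
- Use the visit 2 answer wherever recent exposure enters a Stage 1 device analysis.
- Where the visit 2 answer is missing, keep the donor in analyses based on the eight stable items. Do not treat the visit 1 fitzExpose as exposure at the reading.
- For re-invited donors, use the completion date to decide which answer applies.

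The cost is one extra multiple-choice question in an online form of at most 5 minutes, plus a minor amendment. The item will be missing for donors who do not return the visit 2 form. If the form cannot be changed, the protocol should at least state that Stage 1 fitzExpose will not be used to describe exposure at the reading. That removes the misreading but does not supply the missing information.

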10.1 Invitation

The invitation process will be the same as that described for Stage 1 participants in **Section 9.1.1**. However, Stage 2 participants will receive a modified version of the participant information leaflet (see **Annex 2.18** COMPARE participant information leaflet (Stage 2) V5 21.12.2015).

10.2 Donor screening and informed consent

The donor screening and informed consent process will be the same format as that described for Stage 1 participants in **Section 9.1.2** (however any statements relating to attendance of a 2nd visit are irrelevant). For Stage 2, only the 'study copy' will be completed by the participant and the donor carer. An example 'donor copy' Stage 2 consent form will be provided in the information leaflet that participants receive before joining and can keep for future reference. Stage 2 participants will receive modified versions of the consent forms which refer to the different version of the participant information leaflet (described above) (see **Annex 2.20** COMPARE consent Stage 2 (study copy) V2 20.10.2015) and **Annex 2.18** COMPARE participant information leaflet (Stage 2) V5 21.12.2015) for a donor copy..

10.3 Non-invasive haemoglobin measurement

Following screening, consent process and the standard NHSBT haemoglobin measurements, enrolled donors will have their haemoglobin level re-measured using a non-invasive device. This will be done using either of two hand-held spectrometer devices (ie, MBR Haemospect® versus Orsense NMB200®).

10.4. Research sample collection

The process for the collection of the research samples will be the same as described in **Section 9.1.3**. Donors who have consented to participate in the study will provide 19ml of blood for research (ie, 1 x 4ml EDTA plasma, 1 x 6ml EDTA plasma, 1 x 6ml serum and 1 x TEMPUS tube, requiring 3ml blood).

